## 7.9 Efficacy Analysis

Unless otherwise specified, efficacy analyses will be performed using the FAS and all statistical inference will use a 2-sided 0.05 significance level. Efficacy analyses based on the PPS will also be performed, if appropriate.

The trough sitting clinic SBP/DBP will consist of an average (arithmetic mean) of the non-missing SBP/DBP measurements performed at each visit that satisfy the trough requirements. Post-baseline clinic BP measurements qualify as trough if they are obtained 20-28 hours (inclusive) after the previous study drug dose. Baseline clinic BP measurements are considered trough by default as no double-blind study drug has yet to be taken by subjects.

For the clinic sitting SBP and DBP, missing values will be handled using last observation carried forward (LOCF) methodology. In the LOCF analysis data set, the last observed post-baseline double-blind value will be carried forward and used for all subsequent scheduled time points where data are missing (e.g., the subject has missing data or has dropped out of the study). The efficacy analysis for the response criteria will also be based on the LOCF data set.

## 7.9.1 Primary Efficacy Endpoint

The primary efficacy endpoint, change from Baseline to Week 8 in trough sitting clinic SBP, will be analyzed using an analysis of covariance (ANCOVA) model, with treatment group as a fixed effect and baseline sitting clinic SBP as a continuous covariate. Estimates of treatment LS mean, differences in LS means between TAK-491 treatment groups and valsartan, p-value and 2-sided 95% CIs for the treatment difference will be determined from the framework of the ANCOVA model. For the primary analysis, the overall type 1 error rate of 0.05 will be controlled using the 4-step sequential test described below.

- Step 1: A test for non-inferiority of TAK-491 80 mg to valsartan 160 mg will be performed using a non-inferiority margin of 1.5 mm Hg. If the upper limit of the 2-sided 95% CI of the treatment difference (TAK-491 valsartan) is not greater than 1.5 then proceed to Step 2.
- Step 2: A test for non-inferiority of TAK-491 40 mg to valsartan 160 mg will be performed using a non-inferiority margin of 1.5 mm Hg. If the upper limit of the 2-sided 95% CI of the treatment difference (TAK-491 valsartan) is not greater than 1.5 then proceed to Step 3.
- Step 3: A test for significant difference between TAK-491 80 mg versus valsartan 160 mg will be performed at the 5% level. If the p-value is not greater than 0.05 then proceed to Step 4.
- Step 4: A test for significant difference between TAK-491 40 mg versus valsartan 160 mg will be performed at the 5% level.

Based on historical data, the observed placebo-corrected treatment effects on change from Baseline in clinic SBP for valsartan 160 mg once daily was -8.6 mm Hg [4]. Therefore, the non-inferiority margin was set conservatively at 1.5 mm Hg, which is less than one-third of the valsartan treatment effect. Accordingly, TAK-491 will be considered non-inferior to valsartan

when the upper limit of the 2-sided 95% CI of the treatment difference (TAK 491- comparator) is  $\leq$ 1.5 mm Hg.

The following sensitivity analyses will be performed for the primary endpoint (change from Baseline in trough sitting clinic SBP at Week 8):

- Conduct the described primary analysis in the PPS to explore the robustness of the primary efficacy result.
- A multiple imputation (MI) procedure to assess the impact of missing data and drop-outs for the FAS and PPS. The analysis based on MI assumes the data to be missing at random stratified within each treatment group while retaining consistency for each subject across various visits.
- ANCOVA method which is identical to the primary efficacy analysis, using only the observed case (OC) data for the FAS and PPS.

In addition, the following subgroup analyses will be performed for the primary endpoint where appropriate. Only LOCF data for the FAS will be used:

- gender (males and females).
- age (<45 years, 45 to 64 years, <65 years,  $\ge65$  years and  $\ge75$  years).
- baseline BMI( $<27 \text{ kg/m}^2 \text{ and } \ge 27 \text{ kg/m}^2$ ).
- baseline sitting SBP(140 to <160mm Hg,160 to <180mm Hg and  $\ge$ 180mm Hg).
- baseline sitting SBP (<baseline median and \geqrebaseline median).
- baseline sitting DBP (<90 mm Hg and ≥90 mm Hg).

#### 7.9.2 Secondary Efficacy Endpoints

Change from Baseline in trough clinic sitting DBP at Week 8 will be analyzed using the ANCOVA model described for the primary endpoint in Section 7.9.1, excluding the sequential testing. Baseline sitting clinic DBP will be the continuous covariate in the ANCOVA model. Subgroup analyses and OC sensitivity analyses described for the primary endpoint will also be performed for trough clinic sitting DBP secondary endpoints.

The percentage of subjects responding to treatment and percentage of subjects reaching the target blood pressure at Week 8 will be tabulated for each of the following definitions:

- Response criteria.
  - a) Clinic SBP <140 mm Hg and/or a reduction of  $\geq$ 20 mm Hg from baseline.
  - b) Clinic DBP <90 mm Hg and/or a reduction of ≥10 mm Hg from baseline.
  - c) a and b (e.g., joint criteria).

- Target blood pressure:
  - a) Clinic SBP <140 mm Hg.
  - b) Clinic DBP < 90 mm Hg.
  - c) Clinic SBP <140 mm Hg and DBP <90 mm Hg.
  - d) Clinic SBP <130 mm Hg.
  - e) Clinic DBP < 80 mm Hg.
  - f) Clinic SBP <130 mm Hg and DBP <80 mm Hg.

Response criteria for clinic sitting SBP at Week 8 will be analyzed using a logistic model with treatment group as fixed effect and baseline clinic sitting SBP as a covariate. The odds ratio and its 95% CI will be estimated from the framework of the logistic model. Similarly, a logistic model with treatment as a fixed effect and baseline clinic sitting DBP as a covariate will be used to analyze the response criteria for sitting clinic DBP. The joint response criteria for both clinic sitting SBP and DBP will be analyzed using a logistic model with treatment as a fixed effect and baseline clinic sitting SBP as a covariate. A similar analysis and model will be used to analyze the percentage of subjects reaching target blood pressure at Week 8. The efficacy analysis for the response criteria will be based on the LOCF data set.

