A logistic model with treatment as fixed effect and baseline clinic SBP as a covariate will be used to analyze response for clinic SBP. The odds ratio and its 95% confidence will be estimated. Similarly, a logistic model with treatment as fixed and baseline clinic DBP as a covariate will be used to analyze the response for clinic DBP. The joint response for both clinic SBP and DBP will be analyzed using a logistic model with treatment as fixed effect and baseline clinic SBP as a covariate. A similar analysis and model will be used to analyze the percentage of subjects reaching target blood pressure at Week 8. The percentage of subjects responding to treatment, as well as reaching blood pressure target, will also be presented for other visits, using the above methods.

Subgroups (eg, age, sex) analyses may be performed if data permit.

Sensitivity analyses to be performed on the primary endpoint (and other endpoints where appropriate) include: multiple imputation for missing values; analyses using the per protocol set; and analyses using observed values only.

Safety Analysis:

All safety assessments, including AEs, clinical laboratory test results, vital sign measurements, and 12-lead ECG results will be presented in the data listings. Treatment-emergent AEs will be summarized by treatment group. Laboratory values, pulse rate, and 12-lead ECG results will be summarized with descriptive statistics and/or shift tables.

Sample Size Justification:

Assuming an SD of 17 mm Hg and a 10% dropout rate, a sample size of 200 subjects per treatment group (total of 600 subjects) is sufficient to achieve at least 90% power to detect a difference of 6 mm Hg between TAK-491 dose and valsartan by a 2-sample t-test on the mean change from baseline to Week 8 in mean sitting clinic SBP at 0.05 2-sided significance level. This sample size will also provide, for the above assumptions, at least 90% power for demonstrating noninferiority with a margin of 1.5 mm Hg between TAK-491 and valsartan.

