7.2 Exclusion Criteria

Any subject who meets any of the following criteria will not qualify for entry into the study:

- 1. The subject has a mean, sitting clinic DBP greater than 110 mm Hg at Day 1 (after placebo run in).
- 2. The subject is non-compliant (less than 70% or greater than 130%) with study medication during placebo run-in period.
- 3. The subject has secondary hypertension of any etiology (eg, renovascular disease documented as the cause of hypertension, pheochromocytoma, Cushing's syndrome).

- 4. The subject has a history of myocardial infarction, heart failure, unstable angina, coronary artery bypass graft, percutaneous coronary intervention, hypertensive encephalopathy, cerebrovascular accident, or transient ischemic attack.
- 5. The subject has clinically significant cardiac conduction defects (eg, third-degree atrioventricular block, sick sinus syndrome).
- 6. The subject has hemodynamically significant left ventricular outflow obstruction due to aortic valvular disease and hypertrophic obstructive cardiomyopathy (HOCM).
- 7. The subject has severe renal dysfunction or disease (based on estimated glomerular filtration rate [GFR] <30 mL/min/1.73 m²) at Screening.
- 8. The subject has known or suspected unilateral or bilateral renal artery stenosis.
- 9. The subject has a history of cancer that has not been in remission for at least 5 years prior to the first dose of study drug. (This criterion does not apply to those subjects with basal cell or Stage 1 squamous cell carcinoma of the skin).
- 10. The subject has type 1 or poorly controlled type 2 diabetes mellitus (hemoglobin A1c [HbA1c] >8.5%) at Screening.
- 11. The subject has hyperkalemia (defined as serum potassium above the normal reference range of the central laboratory) at Screening.
- 12. The subject has an alanine aminotransferase (ALT) or aspartate aminotransferase (AST) level of greater than 2.5 times the upper limit of normal (ULN), active liver disease, or jaundice at Screening.
- 13. The subject has any other known serious disease or condition at Screening (or Randomization) that would compromise subject safety, might affect life expectancy, or make it difficult to successfully manage and follow the subject according to the protocol.
- 14. The subject has a history of hypersensitivity or allergies to TAK-491 (azilsartan medoxomil), any of its excipients or other angiotension II (AII) receptor blockers (ARBs).

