## 6.0 DETERMINATION OF SAMPLE SIZE

Assuming a standard deviation (SD) of 17 mm Hg and a 10% drop-out rate, a sample size of 200 subjects per treatment group (total of 600 subjects) is sufficient to achieve at least 90% power to detect a difference of 6 mm Hg between TAK-491 dose and valsartan by a 2 sample t-test on the mean change from baseline to Week 8 in mean sitting clinic SBP at 0.05 2-sided significance level. This sample size will also provide, for the above assumptions, at least 90% power for demonstrating non-inferiority with a margin of 1.5 mm Hg between TAK-491 and valsartan.

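### The joint SBP-and-DBP endpoints are adjusted for baseline SBP only; adding baseline DBP is an optional, low-cost refinement with a small gain

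*SAP*

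**What the plan says.** SAP 7.9.2 fits each single-component endpoint with its own baseline. For DBP change, "Baseline sitting clinic DBP will be the continuous covariate in the ANCOVA model". For DBP response, "baseline clinic sitting DBP as a covariate will be used to analyze the response criteria for sitting clinic DBP". SBP response uses baseline SBP.

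Joint response (criterion c) requires both the SBP and the DBP criterion, yet "SBP and DBP will be analyzed using a logistic model with treatment as a fixed effect and baseline clinic sitting SBP as a covariate". The protocol has the same model in the Study Summary (2.0) and in 13.1.3: "The joint response for both clinic SBP and DBP will be analyzed using a logistic model with treatment as fixed effect and baseline clinic SBP".

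For the target endpoints, which include the joint targets c (<140/90) and f (<130/80), the SAP says only: "A similar analysis and model will be used to analyze the percentage of subjects reaching target blood pressure at Week 8". No covariate is named there, so SBP-only adjustment of c and f is inferred by analogy with joint response. Neither document gives a reason for leaving out baseline DBP.

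**The concern.** Baseline DBP bears directly on the diastolic half of each joint endpoint. Entry requires Day 1 SBP of 150 to 180 mm Hg, so no eligible subject is below 140 systolic at baseline. DBP has only an upper limit of 110 (Protocol 7.2), and SAP 7.5.2 tabulates baseline DBP below 90 against 90 or above. A subject who enters with DBP below 90 already meets the diastolic part of joint response and of the <140/90 target.

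Six Week 8 odds ratios (3 joint endpoints × 2 TAK-491 doses versus valsartan) are therefore not adjusted for a chance imbalance in baseline DBP, while DBP change and DBP response are. The baseline ANOVA in SAP 7.5.2 would show such an imbalance, but no joint analysis visible in the documents adjusts for it. Adding the covariate after unblinding would be post hoc.

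The stakes are limited to precision and interpretation of secondary results. On the error rate, the SAP says: "For the primary analysis, the overall type 1 error rate of 0.05 will be controlled using the 4-step sequential test described below". The joint endpoints are not in that sequence.

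**Working it through.** **1. The plan's own figure.** SAP 6.0 gives SD 17 mm Hg, difference 6 mm Hg, 200 per arm and 10% dropout, so 200 × 0.9 = 180 per arm.

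- SE = 17 × √(2/180) = 1.792. Power = Φ(6/1.792 − 1.96) = Φ(1.39) = 91.7%, which agrees with the stated minimum of 90%.
- Required n = 2 × (1.960 + 1.282)² × 17²/6² = 169 per arm, and 169/0.9 = 188, below 200.

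The primary sizing reproduces. No power is stated for any joint endpoint.

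**2. Simulation.** There is no simple closed form for the joint endpoints. I compared two logistic models on the same simulated trials, one TAK-491 arm versus valsartan, two-sided Wald test at 0.05: treatment + baseline SBP (as planned), and the same plus baseline DBP.

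- From the documents: SD of SBP change 17, SBP effect 6, baseline SBP truncated to 150–180, baseline DBP truncated at 110, 180 per arm.
- Assumed, varied over 24 scenarios: baseline SBP mean 155–165, SD 6–12; baseline DBP mean 85–98, SD 8–11 (means and SDs before truncation); SBP–DBP correlation 0–0.4; slope of change on baseline −0.1 to −0.5; valsartan mean change −12 to −22 systolic and −6 to −12 diastolic; SD of DBP change 8–11; residual correlation 0.4–0.7; DBP effect 2–4 mm Hg.
- Per scenario: 4,000 trials with an effect and 2,000 without (24 × 2,000 = 48,000 null trials).

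| Effect of adding baseline DBP | Joint response c | <140/90 | <130/80 |
|---|---|---|---|
| Power change, points: mean (range) | +0.1 (−0.3 to +0.6) | +0.3 (−0.4 to +1.2) | +0.8 (0.0 to +1.8) |
| Type I error, planned / with DBP | 5.0% / 5.0% | 5.1% / 5.1% | 4.8% / 4.9% |
| Rise in odds ratio | 0.2%–1.2% | 0.2%–2.1% | 0.7%–3.1% |
| Rise in its SE | 0.3%–1.3% | 0.3%–1.9% | 0.7%–2.6% |
| Trials where the p<0.05 decision differs | 0.8%–3.4% | 1.1%–5.1% | 2.4%–6.7% |
| Odds-ratio shift from a 1-in-20 DBP imbalance (median) | 0.9%–5.3% (2.4%) | 1.4%–7.9% (3.6%) | 4.6%–13.4% (7.2%) |
| Largest such shift, as a fraction of the SE | 0.24 | 0.32 | 0.36 |

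The Monte Carlo SE of the mean power change is 0.04, 0.05 and 0.07 points; within a single scenario it is 0.1–0.4 points, so small negative values are noise.

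**3. Size of the imbalance.** A 1-in-20 difference between arms is 1.96 × SD × √(2/180) = 0.207 × SD. After truncation this came to 1.5–2.1 mm Hg.

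**4. Why the gain is small.** In logistic regression an added predictor does not shrink the SE of the treatment effect. It moves the conditional odds ratio away from 1 while the SE also rises a little. Baseline DBP is a modest predictor: log-odds per SD of −0.04 to −0.30 (joint response), −0.07 to −0.37 (<140/90) and −0.21 to −0.54 (<130/80).

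**5. Other assumptions.** With 200 per arm and an assumed baseline DBP mean of 94 and SD 10, power went from 83.8% to 84.0%, 81.6% to 81.9%, and 68.3% to 69.2%. Across variants of that set-up, including DBP SD up to 13 and baseline DBP fully carried to Week 8, the changes ran from −0.3 to +1.0, −0.1 to +2.7 and +0.3 to +4.6 points. Null rejection was 3.9%–4.9% with either model. Runs at 190 per arm gave gains of about 0.4–1.0, 0.3–2.0 and 0.8–2.5 points.

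**The case against.** The strongest reply is that nothing is broken. The model is pre-specified, protocol and SAP agree, randomization makes the unadjusted-for-DBP test valid, and chance imbalance is already part of the variation that the test allows for. That stands in full.

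Second, SBP-only adjustment is written out only for joint response, where the gain is negligible; the visible gain is for <130/80, where the covariate is inferred. That also stands, though naming the covariates would settle the open reading.

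Third, differing p<0.05 decisions go in both directions and do not show that the planned model is worse. Agreed: they are a reason to fix the model in advance, not evidence of a defect.

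Fourth, most inputs are assumed, and the scenario ranges are not bounds, as step 5 shows. Also, LOCF keeps dropouts who have a baseline and any double-blind value, so the analysed number lies between 180 and 200 per arm. At 200 the imbalance is √(180/200) = 0.95 times as large, about 5% smaller. This does not alter the picture.

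Fifth, the text under SAP 7.9.3 is not visible, so the statement that no joint analysis adjusts for DBP applies to the visible text. The planned subgroups by baseline DBP (<90, ≥90) cover SBP and DBP change; they do not adjust the joint odds ratios.

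**Conclusion.** The point holds as an optional refinement. It is not an error, a contradiction or a threat to any primary claim. For joint response the gain is practically nil (mean +0.1 points of power, about 1 point at most in any run). For <140/90 it is usually 1 point or less. For <130/80 it averaged 0.8 points in the main scenarios and exceeded 4 points only when baseline DBP was assumed widely spread and fully carried to Week 8. The other benefit is that a DBP imbalance would be adjusted for under a rule set in advance. These sizes rest on assumed baseline DBP distributions, correlations, slopes and DBP effects that the documents do not give, and for the two joint targets on the natural reading of the model sentence.

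**What to change.** Before unblinding, specify treatment, baseline clinic SBP and baseline clinic DBP in the logistic models for response criterion c and target criteria c and f, for both TAK-491 doses versus valsartan. Name the covariates for the targets explicitly. The protocol applies the same methods at other visits, so the change should carry through there.

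Either amend Protocol 2.0, Protocol 13.1.3 and SAP 7.9.2 together, or amend the SAP and record the departure in SAP 7.12, which now lists none. SAP 3.0 sends changes to principal features to a protocol amendment and other changes to a SAP amendment, so the sponsor must decide which applies.

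The cost is one model term, no new data and the document change. The odds ratio then conditions on DBP as well, so it is a slightly different quantity, with the small rises in the estimate and its SE shown in the table.

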## 7.9.3 Additional Efficacy Endpoints

## 7.9.4 Efficacy Analysis for ABPM Subgroup Subjects

All ABPM related summaries and analyses will be based on OC data for the ABPM Set.

The average and change from baseline ABPM values will be calculated by hour and 2-hour over the entire duration of the ABPM measurements. The following comparisons will be presented in figures:

• Average baseline ABPM values by hour for the 0- to 24-hour interval, final ABPM values by hour for the 0- to 24-hour interval, and change from baseline in ABPM values by hour for the 0- to 24-hour interval.

• Average baseline ABPM values by hour for the 0- to 12-hour interval, final ABPM values by hour for the 0- to 12-hour interval, and change from baseline in ABPM values by hour for the 0- to 12-hour interval.

The analysis of ABPM will be based on the following variables that are obtained by summarizing the individual ABPM measurements, namely, 0- to 24-hour mean ABPM, 0- to 12-hour mean ABPM, daytime mean ABPM, nighttime mean ABPM, peak effect, 22- to 24-hour trough ABPM and trough-to-peak ratios.

The baseline 0- to 24-hour mean ABPM will consist of the average (arithmetic mean) of ABPM measurements over the time period beginning with the first ABPM observation and including all observations recorded over the subsequent 24 hours (any observations that are recorded ≥24 hours after the first observation will be excluded).

The final 0- to 24-hour mean ABPM will consist of the average of ABPM measurements over the time period beginning with the final study medication dose and including all observations recorded over the 24-hour period following that dose.

The baseline 0- to 12-hour mean ABPM will consist of the average (arithmetic mean) of ABPM measurements over the time period beginning with the first ABPM observation and including all observations recorded over the subsequent 12 hours (any observations that are recorded ≥12 hours after the first observation will be excluded). The final 0- to 12-hour mean ABPM will consist of the average of ABPM measurements over the time period beginning with the final study medication dose and including all observations recorded over the 12-hour period following that dose.

The daytime mean ABPM will consist of the average of those ABPM measurements that were included in the respective 24-hour mean ABPM calculations and were also recorded between the hours of 6 AM (inclusive) and 10 PM (exclusive).

The nighttime mean ABPM will consist of the average of those ABPM measurements that were included in the respective 24-hour mean ABPM calculations and were also recorded between the hours of 12 AM (inclusive) and 6 AM (exclusive).

The baseline 22- to 24-hour trough ABPM will consist of the average (arithmetic mean) of ABPM measurements over the time period beginning 22 hours (inclusive) after the first ABPM observation and ending 24 hours (exclusive) after the first ABPM observation.

The final 22- to 24-hour trough ABPM will consist of the average of ABPM measurements over the time period beginning 22 hours (inclusive) after the final study medication dose and ending 24 hours (exclusive) after the final study medication dose.

The peak effect interval was determined for each subject as the 2-hour interval during the 24 hours after dosing in which the maximum decrease from baseline was observed for SBP. Peak effect is defined as the change from baseline to Week 8 in BP values by ABPM during the peak effect interval.

Trough-to-Peak Ratio was calculated as mean trough response divided by peak effect, where trough response is defined as the change from baseline in the mean trough (22- to 24 hour) ABPM to Week 8.

The variables based on ABPM will be presented in summary tables by descriptive statistics (including mean, SD, median, minimum, and maximum). Change from Baseline for the ABPM variables will also be summarized in this fashion.

Change from baseline to Week 8 24-hour mean SBP by ABPM will be analyzed using an ANCOVA model with treatment as a fixed effect and baseline 24-hour mean SBP by ABPM as a covariate for ABPM Set. This analysis will be performed separately for DBP. Similar analyses will be performed for other ABPM parameters:

- 24-hour mean SBP and DBP.
- Trough (22-24h) SBP and DBP.
- Mean daytime (6 AM to 10 PM) SBP and DBP.
- Mean nighttime (12 AM to 6 AM) SBP and DBP.
- Mean SBP and DBP at 0 to 12 hours after dosing.
- Peak SBP and DBP effect

Only observed data will be used for the summary and analyses of ABPM parameters. No imputation will be performed for missing data.

ABPM parameters and ABPM related data collected on the eCRF will be included in the data listings. Raw 24-hour ABPM recordings will not be presented in a listing.

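### SAP 7.9.4 appears to form trough-to-peak ratios per subject, reads the DBP peak from an interval chosen on SBP, and has no rule for a divisor that is near zero or a rise

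*SAP*

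**What the plan says.** All the definitions stand in SAP 7.9.4.

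- **Peak interval.** "The peak effect interval was determined for each subject as the 2-hour interval during the 24 hours after dosing" and the criterion is the interval "in which the maximum decrease from baseline was observed for SBP". The choice is made per subject and on SBP only.
- **Peak effect.** "Peak effect is defined as the change from baseline to Week 8 in BP values by ABPM during the peak effect interval". The list of parameters for ANCOVA includes "Peak SBP and DBP effect", so the quantity is derived for DBP as well, from the same SBP-chosen interval.
- **Ratio.** "Trough-to-Peak Ratio was calculated as mean trough response divided by peak effect". The numerator is the Week 8 change in the average of the readings taken 22–24 h after the dose.
- **Summary.** "The analysis of ABPM will be based on the following variables that are obtained by summarizing the individual ABPM measurements", and the list that follows ends with the trough-to-peak ratios. Then: "The variables based on ABPM will be presented in summary tables by descriptive statistics", with mean, SD, median, minimum and maximum named.

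The section sets no lower bound on the divisor, no rule for a zero or positive divisor, and no arm-level ratio. Protocol 13.1.3 says only that the ratio will be calculated and summarised. The additional-endpoint lists are blank in the public copies. The revised text in Protocol Appendix F names the ratio for both SBP and DBP.

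**The concern.** The trough-to-peak ratio is meant to show whether the effect lasts through the dosing interval. It works only if the divisor is a clear fall in the same pressure.

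For DBP the divisor here is not the DBP peak. It is the DBP change at the time of the largest SBP fall, and nothing prevents it from being close to zero or a rise. Three literal records, with changes in mm Hg, show the result:

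- trough −7, peak interval −1: ratio 7.0
- trough +8, peak interval +2: ratio +4.0, although DBP rose at both times
- trough −6, peak interval +1: ratio −6.0

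If such values are averaged within an arm of about 60, one subject with a divisor of a fraction of 1 mm Hg can decide the arm mean. A subject whose pressure rose can also count as evidence of lasting effect.

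**Working it through.** **Plan's own figure.** None is stated for the ratio, so there is nothing to reproduce. The documents give the subgroup size (about 60 per arm, SAP 4.3) but no ABPM means, SDs or SBP–DBP correlation. Everything below rests on assumed values.

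**Leverage of one subject.** Suppose 59 subjects average a ratio of 0.5, a sum of 29.5. The arm mean exceeds 1 if the last ratio is above 60 − 29.5 = 30.5, and is below 0 if it is under −29.5. A trough change of −6.2 over a peak change of −0.2 gives 31, so the arm mean is (29.5 + 31)/60 = 1.01. A trough of −6 over +0.2 gives −30, so the mean is (29.5 − 30)/60 = −0.01.

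**Simulation A.** Arms of 60, twelve 2-hour intervals. Mean changes: SBP −14 at peak and −9 at trough; DBP −9 and −6, so the true DBP ratio is 6/9 = 0.67. SBP between-subject SD 8–12 and interval noise SD 7–12; DBP SDs 0.65 and 0.7 times these; correlation 0.7. Results across settings:

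- The SBP-chosen interval is not the interval of largest DBP fall in about 59% of subjects.
- The DBP divisor is zero or a rise in about 2–6.5% of subjects.
- The arm mean of per-subject DBP ratios is outside 0–1 in about 15–32% of arms.
- The arm median is never outside 0–1, but is about 0.36–0.51 against the true 0.67.
- With the peak chosen on each subject's own DBP, the arm mean is still outside 0–1 in 3–31% of arms.
- One ratio per arm, with the peak read from the arm-mean DBP profile, has a 95% range no wider than 0.35–0.87.

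**Simulation B, wider assumptions.** 4,000 arms of 60. The true effect declines linearly over the twelve intervals from 1.1 to 0.8 times the mean change, so the true ratio is 0.8/1.1 = 0.73. Columns 2–4 give SBP/DBP in mm Hg.

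| Scenario | Mean change | Between-subject SD | Interval noise SD | Corr. | DBP divisor zero or a rise | Arm-mean DBP ratio, 95% range | Outside 0–1 | Arm median, 95% range |
|---|---|---|---|---|---|---|---|---|
| Middle | −14/−8 | 11/7 | 8/6 | 0.7 | 4.4% | −2.45 to 3.07 | 27% | 0.30–0.63 |
| Low noise | −14/−8 | 8/5 | 6/4.5 | 0.8 | 1.2% | −0.71 to 1.49 | 11% | 0.35–0.60 |
| Low correlation | −14/−8 | 11/7 | 8/6 | 0.5 | 7.8% | −3.70 to 3.89 | 35% | 0.37–0.75 |
| Larger effect | −20/−12 | 11/7 | 8/6 | 0.7 | 1.5% | −0.64 to 1.51 | 10% | 0.41–0.65 |
| Smaller effect | −10/−6 | 11/7 | 8/6 | 0.7 | 7.0% | −3.41 to 4.36 | 36% | 0.26–0.62 |
| Larger effect, low noise | −20/−12 | 8/5 | 6/4.5 | 0.8 | 0.2% | 0.30 to 0.69 | 2% | 0.45–0.64 |

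In the middle scenario, the chance that an arm has at least one subject whose DBP divisor is a rise or within 2 mm Hg of zero is 98.7%. That corresponds to about 7% per subject, since 1 − 0.93^60 = 0.987.

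**Separating the two causes (middle scenario).**

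| Ratio averaged over subjects | Divisor zero or a rise | Arm mean, 95% range |
|---|---|---|
| DBP, interval chosen on SBP | 4.4% | −2.45 to 3.07 |
| DBP, interval chosen on DBP | 1.1% | −1.20 to 1.77 |
| SBP, interval chosen on SBP | 1.2% | −1.04 to 1.55 |

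Choosing the interval on DBP narrows the range but does not make the mean usable. The SBP ratio has the same weakness to a lesser degree.

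**Arm means with the SAP's own peak.** Dividing the arm-mean DBP trough change by the arm mean of the SBP-chosen DBP peaks is stable (95% range 0.30–0.56 in the middle scenario), but its centre of 0.44 is well below 0.73. The arm-level ratio therefore also needs its peak taken from the arm-mean profile.

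**The case against.** **The level of the ratio is inferred.** The SAP says that the interval is set for each subject; it does not say so of the ratio. Its reference to mean trough response could be read as an arm mean, and the plural form fits SBP and DBP as well as it fits subjects. A reader might infer that the SAP expressly prescribes a per-subject ratio, but the text does not go that far. The per-subject reading is still the likelier one: the divisor is defined per subject, the trough mean is elsewhere in the section an average of readings over the 22–24 h window, and an SD, minimum and maximum need one ratio per subject. If an arm-level ratio was meant, the SAP must say so and say how the arm's peak is found.

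**The median is planned.** This is correct, and it matters: the median stayed within 0–1 in every scenario. It was also low, centred at 0.45–0.55 in Simulation B against a true 0.73. It is a steady summary but does not recover the ratio.

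**The components are already reported.** ANCOVA of trough and peak, and hourly change profiles, let a reader judge duration directly. This stands and limits the harm, although the reported DBP peak is still the SBP-timed one.

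**Definitions may be elsewhere.** SAP 7.1.2 leaves derived-variable definitions to dataset specifications that are not public. A divisor rule could be there, but a rule that settles what the ratio means belongs in the SAP.

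**Low stakes.** The ratio has no test, interval or decision rule attached. This stands in full.

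**Conclusion.** The point holds as a minor one. On the likelier reading, SAP 7.9.4 averages per-subject ratios without protecting the divisor, and for DBP it takes that divisor from an interval chosen on SBP. The mean DBP ratio would then fall outside 0–1 in roughly 15–32% of arms of 60, or 2–36% under the wider assumptions. In one favourable scenario of six (large effect, low noise, correlation 0.8) the mean was usable. All these figures depend on assumed ABPM variability.

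Three stronger conclusions might be inferred, and none is supported:

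- The SBP-based choice of interval is not the whole cause. Averaging individual ratios is a main cause, it affects SBP too, and it persists when the peak is chosen on DBP.
- The DBP summary as a whole is not uninterpretable. The median is stable and the components are reported by arm.
- The trial's main conclusions are not touched. The ratio is a descriptive variable in a subgroup of about 60 per arm, outside the primary and secondary tests.

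**What to change.** In SAP 7.9.4, before unblinding:

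1. Define the DBP peak on the DBP profile, not on SBP. This also makes the DBP peak effect in the ANCOVA list match its label.
2. State the level of the ratio: one per arm for SBP and one for DBP. Each is the arm-mean change at 22–24 h divided by the arm-mean change in the 2-hour interval where the arm-mean profile of that same pressure falls most. Give a bootstrap CI.
3. If individual ratios are kept, report only their median and quartiles, with the number of subjects whose peak change is zero or a rise. Drop their mean and SD.

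Step 1 alone is not enough, because the mean of individual ratios stays unstable.

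Cost: a few lines of SAP text and a short bootstrap program. No mean of individual ratios would be reported.
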